**[F]Fluciclovine and [F]FLT PET/CT Assessment of Primary High-Grade Brain Tumors**

IMAGING VISIT 1 (Baseline):  IMAGING VISIT 2 (Follow-up):

IMAGING VISIT 3 (Pseudoprogession):

The infusion and imaging procedure will be terminated in any patient who exhibits anaphylaxis, significant hypotension (systolic blood pressure less than 80 mmHg, dyspnea, chest pain, grand mal seizure or an O2 saturation lower than 80%.

Administered dose of [F]FLT \_\_\_\_\_ mCi

Specific Activity of [F]FLT \_\_\_\_\_ Ci/mmol

Initials of Person Making Assessment	Time	Study	Temp	BP	HR	Weight	Height
		Baseline					
		End of Study				NA	NA

Completed by: \_\_\_\_\_

Date: \_\_\_\_\_

PI Signature: \_\_\_\_\_

Date: \_\_\_\_\_

**APPENDIX D: [F]Fluciclovine Infusion Flow Chart for Staff**

Subject Name and MRN: \_\_\_\_\_ Subject Study ID (if enrolled): \_\_\_\_\_

Projected Study Start Date: \_\_\_\_\_ Referring MD: \_\_\_\_\_

**[F]Fluciclovine and [F]FLT PET/CT Assessment of Primary High-Grade Brain Tumors**

IMAGING VISIT 1 (baseline):  IMAGING VISIT 2 (follow-up):

IMAGING VISIT 3 (Pseudoprogession):

The infusion and imaging procedure will be terminated in any patient who exhibits anaphylaxis, significant hypotension (systolic blood pressure less than 80 mmHg, dyspnea, chest pain, grand mal seizure or an O2 saturation lower than 80%.

Administered dose of [F]Fluciclovine \_\_\_\_\_ mCi

Specific Activity of [F]Fluciclovine \_\_\_\_\_ Ci/mmol

Initials of Person Making Assessment	Time	Study	Temp	BP	HR	Weight	Height
		Baseline					
		End of Study				NA	NA

Completed by: \_\_\_\_\_

Date: \_\_\_\_\_

PI Signature: \_\_\_\_\_

Date: \_\_\_\_\_

**APPENDIX E: [F]FLT Patient Adverse Event Questionnaire**

Subject Name and MRN: \_\_\_\_\_ Subject Study ID (if enrolled): \_\_\_\_\_

Projected Study Start Date: \_\_\_\_\_ Referring MD: \_\_\_\_\_

IMAGING VISIT 1 (baseline):  IMAGING VISIT 2 (follow-up):  IMAGING VISIT 3 (Pseudoprogression):

POSSIBLE ADVERSE EVENT	Y =Yes N = No	Comment on possible AE
Body as a Whole:		
Pain (Abdominal)		
Pain (Chest/Breast)		
PAIN (OTHER SITE)		
Fever		
Injection site reaction		
Cardiovascular System:		
Vasodilation (flushing)		
Digestive System:		
Nausea		
Diarrhea		
Vomiting		
Respiratory System:		
Dyspnea (Shortness of breath)		
Skin and Appendages:		
Rash		
Pruritus (Itching)		
Urticaria (Hives)		
Sweating		
Cyanosis (discoloration of fingers/toes)		
Central Nervous System		
Visual disturbances		
Numbness of feet		
Numbness of fingers/hands		
Weakness of feet		
Weakness of fingers		
Burning sensation in feet		
Burning sensation of fingers		

Performed by: \_\_\_\_\_

Date: \_\_\_\_\_

PI Signature: \_\_\_\_\_

Date: \_\_\_\_\_

### APPENDIX F: [F]Fluciclovine Patient Adverse Event Questionnaire

Subject Name and MRN: \_\_\_\_\_ Subject Study ID (if enrolled): \_\_\_\_\_

Projected Study Start Date: \_\_\_\_\_ Referring MD: \_\_\_\_\_

IMAGING VISIT 1 (baseline):  IMAGING VISIT 2 (follow-up):  IMAGING VISIT 3 (Pseudoproggression):

POSSIBLE ADVERSE EVENT	Y =Yes N = No	Comment on possible AE
Body as a Whole:		
Pain (Abdominal)		
Pain (Chest/Breast)		
PAIN (OTHER SITE)		
Fever		
Injection site reaction		
Cardiovascular System:		
Vasodilation (flushing)		
Digestive System:		
Nausea		
Diarrhea		
Vomiting		
Respiratory System:		
Dyspnea (Shortness of breath)		
Skin and Appendages:		
Rash		
Pruritus (Itching)		
Urticaria (Hives)		
Sweating		
Cyanosis (discoloration of fingers/toes)		
Central Nervous System		
Visual disturbances		
Numbness of feet		
Numbness of fingers/hands		
Weakness of feet		
Weakness of fingers		
Burning sensation in feet		
Burning sensation of fingers		

Performed by: \_\_\_\_\_

Date: \_\_\_\_\_

PI Signature: \_\_\_\_\_

Date: \_\_\_\_\_

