**Expected risks to subjects participating in clinical studies:** No serious adverse reactions have been reported from any investigator sponsored studies or from the compassionate use program in Norway. The risks to subjects mainly relate to the intravenous injection and intravenous blood sampling procedures, and the radiation emitted by [F]Fluciclovine. Intravenous injection and the use of an intravenous cannula are known to carry a small risk of infection and hematoma. The exposure to radiation will not exceed that which is considered acceptable in accordance with appropriate guidelines.

AEs arising from the industry-sponsored studies described above which are considered to be potential adverse reactions to [F]Fluciclovine are listed in Table 1. Of these events, dysgeusia, headache, redness at the injection site, and sensation of burning during injection are considered to be adverse drug reactions potentially related to the investigational product and are included in the summary Table 1 below (Reference Safety Information). [F]Fluciclovine remains under clinical investigation. Investigators should be alert to the potential for additional adverse reactions to be observed as clinical experience continues

(F)Fluciclovine Investigator’s Brochure, Version 05; May 30, 2017 and Axumin prescribing information 2016). Based on the pharmacokinetics of [F]Fluciclovine and of AH114760, the safety reporting window for monitoring for potential adverse reactions is set at 28 days post injection.

Table 1. Reference Safety Information

System organ class/Preferred term	Frequency Number of Subjects (%) Total N = 1153	Intensity		
		Mild	Moderate	Severe
Any Event	12 (1%)	12	0	0
General disorders and administration site conditions	7(0.6%)	7	0	0
Injection-site reactions	7 (0.6%)	7	0	0
Nervous system disorders	4 (0.3%)	4	0	0
Dysgeusia	4 (0.3%)	4	0	0
Respiratory Organ, Thoracic and Mediastinal Disorders	2 (0.2%)	2	0	0
Parosmia	2 (0.2%)	2	0	0

\*1 patient reported both dysgeusia and parosmia

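### The fluciclovine adverse-event form repeats the FLT form and has no specific item for altered taste, altered smell or headache, and section 3.1.4 disagrees with its Table 1 on whether headache is a reference reaction

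*Combined protocol and SAP*

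**What the plan says.** The protocol provides one adverse-event questionnaire per tracer: Appendix E for FLT and Appendix F, the "Fluciclovine Patient Adverse Event Questionnaire". Both have tick boxes for imaging visits 1 to 3, a yes/no column and a comment column.

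Section 3.1.4 states of fluciclovine that "dysgeusia, headache, redness at the injection site, and sensation of burning during injection are considered to be adverse drug reactions potentially related" to the product, and says that these are included in Table 1, the Reference Safety Information. Table 1 lists three preferred terms in 1153 subjects: injection-site reactions (7), dysgeusia (4) and parosmia (2). The total with any event is 12, all mild, and a footnote says that "1 patient reported both dysgeusia and parosmia".

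Two other sections bear on the point. Section 8.4.1 asks for events to be sought by non-directive questioning and accepts those that patients volunteer or that other assessments reveal. Table 5 in section 8.6.1 makes reporting of grade 2-3 events depend on whether the event is expected.

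**The concern.** A tracer-specific checklist should prompt for the reactions known for that tracer. Appendix F appears to be the FLT form under a new title. Six of its 22 items ask about numbness, weakness or burning in the hands and feet, down to "Burning sensation of fingers". These fit FLT, for which section 3.1.2 reports peripheral neuropathy; section 3.1.4 names no such reaction for fluciclovine. Taste, smell and headache have no line of their own.

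Two things are at stake. Mild, short-lived reactions that are not prompted by name may go unrecorded after any fluciclovine scan, of which a patient can have up to three. Also, the document that defines expectedness contradicts itself on headache, which section 2.1 counts among the most common symptoms of brain tumors. Staff applying Table 5 could reach opposite answers for the same event.

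**Working it through.** **Comparison of the forms.** Read side by side, Appendices E and F match on 22 of 22 items, in wording and order.

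**Named reactions against the form.**

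| Reaction | 3.1.4 sentence | Table 1 row | Appendix F item |
|---|---|---|---|
| Injection-site redness | yes | within injection-site reactions (7) | yes, injection-site reaction |
| Burning during injection | yes | plausibly within the same row | plausibly the same item |
| Dysgeusia | yes | yes (4) | none |
| Parosmia | no | yes (2) | none |
| Headache | yes | none | none by name; could be written under the generic other-site pain line |

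Two of the three preferred terms in Table 1 therefore have no item.

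**Reproducing Table 1.** Events: 7 + 4 + 2 = 13. One subject is counted under both dysgeusia and parosmia, so subjects = 13 − 1 = 12, which is the stated total; 12/1153 = 1.04%, stated as 1%. Subjects with a taste or smell reaction = 4 + 2 − 1 = 5. Since 7 + 5 = 12, the injection-site group and the taste/smell group do not overlap. So 5/12 = 41.7% of reacting subjects had only reactions without an item, and 7/12 = 58.3% had the reaction that the form does ask about. Of all subjects, 5/1153 = 0.43% had a taste or smell reaction.

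The three rows account for every subject in the total, and the four dysgeusia subjects account for the whole nervous-system class. There is no subject left over for a headache-only row, so a row lost in reproducing the table is an unlikely explanation.

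**What could be seen in this trial.** Assume the reference rate of 5/1153 applies per patient (30 patients) or, at the extreme, per scan with scans independent (3 × 30 = 90, which assumes every patient has all three sessions).

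- 30: expected 30 × 5/1153 = 0.13 cases; chance of at least one = 1 − (1 − 5/1153)^30 = 12%.
- 90: expected 90 × 5/1153 = 0.39 cases; chance of at least one = 1 − (1 − 5/1153)^90 = 32%.

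**Expectedness of headache.** Take a grade 2 or 3 headache after a fluciclovine injection, judged possibly related, without hospitalization.

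- By the 3.1.4 sentence, headache is a reference reaction and so expected. Table 5 then requires no expedited report.
- By Table 1, headache is absent and so unexpected. Table 5 then requires an expedited report within 7 working days.

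Nothing else settles it. The opening of section 8 sends the reader to section 6 for the list of adverse events, but section 6 covers imaging methods. Section 9.2.2 refers back to 3.1.4 and does not mention headache.

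**The case against.** The strongest defence is that the form is not the only safeguard and the omitted events are minor. Much of this stands.

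- A reader might infer that fluciclovine's reactions are not asked about at all, or that the form covers only FLT's risks. The documents do not support that. Injection-site reaction, the most frequent entry in Table 1, is on the form; redness falls under it and burning during injection plausibly does. Sixteen of the 22 items are not limb-neuropathy items and are mostly general.
- A reader might infer that recorded frequencies are biased toward zero, or that a comparison with reference rates is lost. Neither is shown. Section 8.4.1 requires open questioning and collects events for 24 hours after each injection whatever their cause. Section 5.6.1 also requires questioning after each administration. Headache can be written under the generic pain line. No objective or analysis in section 7.2 compares adverse-event rates, and with 0.13 to 0.39 expected taste or smell cases even a complete form would say little about them.
- The headache conflict is narrow. Section 8.4.1 counts a pre-existing condition only if it worsens after injection. Table 5 requires no expedited report for grade 1 on either reading, and requires a report of any grade 3-5 event leading to hospitalization whether expected or not. Expedited reporting to the FDA under 8.5 also needs the event to be serious.

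This does not dispose of the point. Having chosen a yes/no checklist per tracer, the plan gives fluciclovine one that prompts for six neuropathy-type symptoms and omits two of its three reference terms. A pain line cannot capture altered taste or smell. Open questioning does nothing to reconcile 3.1.4 with Table 1.

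**Conclusion.** The point holds as two modest defects. First, Appendix F duplicates the FLT form and lacks specific items for dysgeusia, parosmia and headache. Reactions without an item were the only ones in 5 of 12 reacting reference subjects, but that is 0.43% of the 1153, and all were mild. The consequence is a risk of under-recording, partly offset by open questioning. Second, the 3.1.4 text and Table 1 disagree: headache is in the sentence but not the table, and parosmia is in the table but not the sentence. For headache this gives two answers under Table 5, confined to grade 2-3 events judged at least possibly related and not involving hospitalization.

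The counts rest on Table 1 reporting subjects per term, as its column heading says, and on the footnote describing the only overlap, which the total of 12 confirms. The projection to this trial assumes that the reference rate carries over to brain-tumor patients. Efficacy endpoints, sample size and significance levels are untouched.

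**What to change.** In Appendix F, add three lines: altered taste, altered smell, and headache that is new or worse than before the injection. The last wording follows the worsening rule in 8.4.1. A separate line for burning or redness at the injection site is largely redundant. The limb items can stay.

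In section 3.1.4, reconcile the sentence and Table 1 for both headache and parosmia against the source of the Reference Safety Information, so that Table 5 gives one answer. Which of the two is right is for the sponsor to establish. Correct the pointer at the start of section 8 so that it leads to the list actually used.

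The cost is a few lines on a short form, one sentence or table row, and an amendment for IRB approval under 8.7. The small downside is that more background headache will be recorded and will need attribution; asking only about new or worsened headache limits this.

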**APPENDIX G: NCI Common Toxicity Criteria**

[https://ctep.cancer.gov/protocolDevelopment/electronic\\_applications/docs/CTCAE\\_v5\\_Quick\\_Reference\\_5x7.pdf](https://ctep.cancer.gov/protocolDevelopment/electronic_applications/docs/CTCAE_v5_Quick_Reference_5x7.pdf)
